1.2 Investigational Device

DS8R Isolated Biphasic Constant Current Electrical Stimulator (Digitimer Ltd)

Abbott percutaneous trial lead for epidural neurostimulation (Model 3086)

Abbott clinician programmer for epidural neurostimulation (Model 3874)

Ripple Nomad Neurostimulator

The temporary percutaneous implantation of epidural stimulation electrode leads will be surgically implanted to activate lumbosacral spinal networks in four humans diagnosed with chronic, complete, or incomplete loss of motor function below the level of SCI. By delivering electrical stimulation over the spinal cord during rehabilitation we aim to compare electrophysiological activity produced by spinal sensorimotor networks in response to transcutaneous or percutaneous epidural stimulation and quantify changes in motor performance metrics over the course of 12 motor rehabilitation sessions with either transcutaneous or percutaneous epidural stimulation.

1.3 Preclinical Data

Several decades of human investigation have focused on using ES to activate what was thought to be isolated spinal circuitry below the level of functionally complete SCI in order to study central pattern generator activity (Dimitrijevic et al. 1998; Jilge et al. 2004; Minassian et al. 2004; Roy et al. 2012) In 2011, Harkema and colleagues published a landmark report that after months of training, ES facilitated intentional control of joint-specific muscles and independent standing by a human with motor complete paraplegia (Harkema et al. 2011). The same research group successfully replicated their results in three additional subjects (Rejc et al. 2015; Rejc et al. 2017; Angeli et al. 2014). Based on these results, we initiated a clinical trial (NCT02592668) and in 2017, we reported successful replication of Harkema et al., along with additional outcomes (Grahn et al. 2017). Based on observations made during NCT02592668, we have designed this protocol to gain additional scientific knowledge with respect to mechanisms by which TS and ES enables functions in humans.

In addition to studying ES as described in this protocol, we intend to gather comparative data from the non-invasive spinal neuromodulation approach known as transcutaneous electrical spinal stimulation (TS). Prior evidence has shown that TS generates patterned motor activity and limb movements in healthy humans (Gerasimenko et al. 2016; Gerasimenko et al. 2015; Minassian et al. 2007; Minassian et al. 2007). More recently, TS has been reported to enable motor function in humans with SCI (Inanici et al. 2018; Gerasimenko, Lu, et al. 2015).

Our Mayo team recorded preliminary TS data in two subjects during supine activities prior to ES implantation. TS-evoked responses were recorded during low-frequency TS to investigate spinal sensorimotor activity generated to produce leg muscle activity. We compared responses across TS and ES. Preliminary data indicate smaller latency from stimulation to response in ES when compared to TS, indicating different mechanisms of action may underlie each approach. However, more subjects need to be investigated with a more structured study design to determine key differences between TS and ES. Completion of the proposed experiments in this protocol will provide data that can be used to improve the scientific understanding of how each technique enables function after SCI. This knowledge will be used to design future investigations that focus on safety and therapeutic efficacy of TS and ES.

1.4 Study Rationale and Risk Analysis (Risks to Benefits Ratio)

1.4.1 Study Rationale

There is no cure for SCI, which results in permanent loss of movement and sensation in body regions below the level of injury and a significant reduction in quality of life for SCI survivors. To address the lack of curative options following SCI, research efforts over the past decade have led to the development of neuromodulation approaches, such as TS and ES to activate spinal cord circuitry below the injury and enable lost functions. Scientific investigations of small numbers of humans with SCI have demonstrated positive functional outcomes such as standing, stepping, enhanced bladder function, and improved cardiovascular function, can be achieved using spinal stimulation. However, from a scientific perspective, the spinal sensorimotor circuitry activated using TS or ES has yet to be directly compared. Additionally, subjects need to be investigated within a structured study design to better understand the effect of rehabilitation on TS and ES enabled functions. Completion of the proposed experiments in this protocol will provide data that can be used to improve the scientific understanding of how each technique enables function after SCI. This knowledge will be used to help determine if TS is a viable and useful tool in determining which subjects may be best suited for ES through a clinical service line.

1.4.2 Anticipated Risks

Risks associated with rehabilitation:

In combination with TS and ES, the rehabilitation techniques used during this study will focus on maximizing independence, load bearing, body position, and kinematics during motor tasks while providing the minimum amount of trainer assistance and body weight support necessary to safely perform tasks. Risks associated with daily training include skin irritation and minor bruising from pressure applied during trainer assistance and body weight support, musculoskeletal discomfort, fatigue, and bladder or bowel incontinence due to

exertion and abdominal pressure from support harness. There is a slight risk of fracture in the lower extremities. Orthostatic hypotension is a risk associated with abrupt position changes against gravity, specifically transitioning from sit to stand quickly.

Risks associated with weight-bearing tasks:

Risks include muscle soreness, fatigue, skin irritation, fracture, changes in blood pressure, and potential for a fall.

Risks associated with TS:

Skin irritation due to electrical current passing through human tissue, skin irritation due to adhesives used to apply skin surface electrodes, discomfort or abdominal tightness during TS, increased or decreased spasticity, bowel or bladder incontinence, shortness of breath, muscle soreness, or fatigue may occur. Autonomic dysreflexia is a risk for those with midthoracic or higher-level injuries. Skin irritation or burns may occur during high-amplitude stimulation and/or prolonged stimulation sessions; skin breakdown may also occur as a result of this stimulation, with ensuing infection being a potential risk.

Risks associated with temporary percutaneous implantation of ES electrode leads:

ES electrodes will be implanted via commonly used percutaneous implantation techniques for FDA-approved treatment of medically refractory pain conditions. Therefore, the risks associated with percutaneous implantation of the ES system for this study match the risks associated with ES system implantation for treatment of FDA-approved conditions.

- Undesirable changes in stimulation may occur over time. These changes in stimulation are possibly related to cellular changes in tissue around the electrodes, changes in the electrode position, loose electrical connections and/or lead failure.
- Placement of a lead in the epidural space is a surgical procedure that may expose the patient to risks of epidural hemorrhage, hematoma, infection, spinal cord compression, and/or paralysis.
- Radicular chest wall stimulation.
- Cerebrospinal fluid (CSF) leakage.
- Persistent pain at the electrode site or receiver site.
- Seroma at the incision site, as well as serosanguinous drainage.
- Implant migration.
- Allergic or rejection response to implant materials.
- Lead migration and/or local skin erosion.
- Paralysis, weakness, clumsiness, numbness, or pain below the level of implantation.

Risks associated with ES following implantation:

Hardware malfunction, discomfort, or abdominal tightness during ES, increased or decreased spasticity, bowel or bladder incontinence, shortness of breath, muscle soreness, or fatigue may occur during ES. Autonomic dysreflexia is a risk for those with mid-thoracic or higher-level injuries.

Risks associated with MRI

Dislodgement of some metal implants and claustrophobia may occur during MRI. Subjects will be rigorously screened in the same fashion as clinical patient by MRI technicians prior to each scan. Earplugs will also be provided to keep MRI noise within a safe audible range. Due to the potential for tissue heating, image artifacts, induced voltages in the neurostimulator or leads, and lead dislodgement, MRIs will not be obtained after epidural stimulator implantation.

Risks associated with Transcranial magnetic stimulation

Transcranial magnetic stimulation is electrical pulses from the magnet to the brain. Risks are possible hearing changes, headache, and a chance of heating on the skull where the magnet is placed.

Risks associated with electromyography and electroneurography

Risks involved with EMG include skin irritation or allergic reaction from the adhesive used to apply sensors. Additionally, electroneurography carries the risk of pain and discomfort from needle placement, and infection at the needle stick site.

Risks associated with urodynamic studies

Urodynamic studies may carry the risk of autonomic dysreflexia, mild irritation of the urethra, and infection.

Steps taken to minimize the occurrence and severity of associated risks:

Trained study staff and medical technicians will directly oversee all tasks. Body weight support, a safety gait belt, and other safety measures as necessary will be utilized to lessen the risks involved with rehabilitation and weight-bearing tasks. Transcutaneous electrode sites will be checked routinely throughout rehabilitation sessions, and if skin irritation or damage is observed, no further stimulation will occur until the site has healed. To mitigate risks in general, the protocol will be conducted as stated, medical professionals will be consulted, and care will be provided to address any study-related concerns that arise. All members of the research team will be trained to identify the occurrence of risks related to this study. If risk occurrence is observed, study-related activities will be halted until appropriate medical care is given and it is deemed safe for the subject to continue study-related activities. Because the interventions have been used for individuals with spinal cord injury and subjects will have been carefully screened, we do not anticipate any serious adverse events in this study. However, if they do occur, serious adverse events will be reported to the PI, medical monitor, IRB, and FDA within the appropriate reporting timeframes. Adverse events will be reported to the PI, the site medical monitors IRB, and FDA within the appropriate reporting timeframes.

1.4.3 Potential Benefits

The benefits which may result from this research study may include recovery of sensorimotor function below the level of SCI, recovery of bladder, bowel, or sexual function, improved thermoregulation, improved body mass composition, and improved sense of wellbeing. The certainty and degree to which these benefits may or may not occur is unknown.

1.5 Anticipated Duration of the Clinical Investigation

The anticipated duration of study participation for each human subject is approximately 6 months. During the 6 months, subjects will complete either TS rehabilitation sessions for the 1 month, or ES rehabilitation sessions for 1 month. After 1 month of either TS or ES, subjects will be followed for an additional 4 months for follow-up assessments. ES electrodes will be removed following 1 month of rehabilitation sessions.

2 STUDY OBJECTIVES

We propose to compare motor activity and clinical outcomes over the course of 1 month of TS or ES in combination with physical rehabilitation.

2.1 Primary Objective

The primary outcome data collected will be used to compare spinal sensorimotor activity in muscles below the level of injury during TS or ES-enabled motor tasks in persons with chronic motor complete paralysis of the lower extremities due to traumatic SCI.

2.2 Secondary Objective

Quantify changes in motor performance metrics over the course of 12 motor rehabilitation sessions with transcutaneous or percutaneous epidural stimulation

3 STUDY DESIGN

3.1 General Design

This is a pilot study that will include a total of 8 subjects with chronic, motor complete or incomplete paralysis below the level of SCI. All subjects will complete either 1 month of TS or ES driven physical rehabilitation sessions (**Table 1**). All subjects will then be followed for an additional 4 months for follow-up assessments. Expected duration of subject participation is less than 6 months.

Table 1: Study Design

	PRE-INTERVENTION	INTERVENTION	POST-INTERVENTION	Follow-Up					
Subjects	Baseline Assessments	Minimum 12 Sessions	ents	Assessments					
50% of Sub	Clinical, Electrophysiology, Kinematic Assessments & Surveys	Stimulation + Motor Training	Training Kinematic Assessments						
	Tr	Kinematic	Kinematic veys	END					
	DDE INTERVENTION					∠			
	PRE-INTERVENTION	INTERVENTION	POST-INTERVENTION	Sul	ogy, Sur				
jects	Baseline Assessments	Minimum 12 Sessions		nysiology, & Sul	nysiology, & Sur	STUDY			
50% of Subjects		Minimum 12 Sessions Stimulation + Motor		Electrophysiolc &	Electrophysiolo &	STUD			
₽	Baseline Assessments Clinical, Electrophysiology, Kinematic Assessments & Surveys	Minimum 12 Sessions Stimulation + Motor	End Assessments Clinical, Electrophysiology, Kinematic Assessments & Surveys	Clinical, Electrophysiology, & Su	Clinical, Electrophysiology, & Sur	STUD			

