3.2 Primary Study Endpoints

Due to the pilot phase design of this clinical trial, it is not feasible to designate primary study endpoints. With this in mind, we do consider the biomechanical assessments and electrophysiology tests to be the primary sets of endpoints used to quantify TS and ES-related datasets associated with addressing the specific aims of this proposal.

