6 STUDY PROCEDURES

6.1 Screening:

Subjects will complete a variety of assessments and procedures to determine their enrollment eligibility. When possible, eligible subjects will have their screening data used as baseline data collection. Primary outcomes include biomechanical assessments related to motor tasks, electrophysiology tests, and an ASIA examination. Secondary outcomes include spasticity assessments, subjective surveys, and various spine imaging.

6.2 Intervention 1: Transcutaneous Electrical Spinal Stimulation (TS) and Task Specific Training Sessions

Subjects will report to the ART lab at St. Mary's Hospital for daily sessions of TS and task-specific training interventions. TS stimulation will be applied to the skin surface over the spine as described previously.

Training sessions will begin upon completion of baseline testing. Subjects will participate in a 3 days per week training regimen over 1 month with a goal of achieving 12 sessions. Activities include tasks specific to supine intentional leg movement training, balance training, stand and step (reciprocal flexion/extension) training. Heart rate will be recorded prior to, and after, each session, and at any time the intervention is paused due to a concern. Environments include the body weight support treadmill (BWST) system to allow trainer-assisted stand and step activities as needed, custom standing frame, and a hi/lo mat for supine

and seated activities. As the subjects progress their intentional motor ability with standing and stepping, BWS will be removed, and assist will continue to be provided on an as needed basis. Any visit to the laboratory when TS is enabled will be considered a training session. Activities chosen for each session will be based on the subject's progression.

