6.6 Outcome Measures

The following outcome measures will be collected as scheduled in **Table 3** with tests occurring over an approximately one-week period of time for each time point. Photographic and video images will be recorded throughout the study, but will not be shown to anyone outside the study team without the subject's written consent.

6.6.1 Primary:

Biomechanical assessments

During a variety of tasks including supine, side-lying, reaching, standing, and stepping activities, kinematics, EMG, and foot pressure measurements may be obtained, with or without spinal stimulation, using the following metrics:

Kinematics: We will use commercially available_markers placed on the skin surface via a non-irritant adhesive to record limb movement and joint angles. Available systems we may use include video-based, inertial measurement units, electromagnetic.

Electromyography: We will collect muscle activity using skin surface electrodes placed at anatomical locations of muscle groups below the level of injury. Activity will be recorded using a 16-channel signal amplifier and data acquisition system (PowerLab, ADInstruments, Colorado). At locations where self-adhesive bipolar recording electrodes will be placed onto the skin, the area will be cleaned with alcohol to ensure secure attachment and enhance signal recordings. A subset of the following muscles or muscle groups will be tested: soleus, gastrocnemius, tibialis anterior, hamstrings, quadriceps, hip adductors, gluteus maximus, gluteus medius, abdominals, triceps, trapezius, and spinal extensors.

Foot pressure: Foot pressure will be measured with shoe-insole pressure sensors (F-SCAN, Tekscan Inc., Boston, MA).

Seated pressure: Seated pressure will be assessed via a force sensing array placed beneath the buttocks (Vista Medical BodiTrak force sensing array, Winnipeg, MB, Canada).

Over the course of rehabilitation, if the research team observes stimulation-enabled functions that could be enhanced by further optimization of stimulation parameters, biomechanical assessment equipment may be used during select rehabilitation sessions in addition to the main assessment timepoints described in **Table 3**.

Table 3: Outcom	e Measure	es								
			Stı	ıdy Tin	neline					
	Screening	Pre	Implant	Spinal Stimulation + Motor training			Explant	Post	Follow-Up	
Weeks	0	Baseline		1	2	3	4		5	8, 20
Motor Training				X	X	X	X			
Urinalysis	X									
DEXA ¹	X									

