		P	rin	nary Ou	ıtcome	es				
Kinematics ²				X			X			X
EMG ²		X		X			X		X	X
SSEPs		X							X	X
TMS MEPs		X							X	X
TMS + ES or TS2		X							X	X
TS MEPs	X								X	X
ES MEPs				X			X			
BBS, TUG, 6MWT		X							X	X
FRT/mFRT				X			X			X
ISNCSCI	X								X	X
Secondary Outcomes										
Spine CT or MRI	X			X			X			
Urodynamic Studies		X							X	
Surveys		X							X	X

^{1.} DEXA scan measured at either left or right femur, and AP spine; not to include total body scan.

DEXA=Dual Emission X-ray Absorptiometry, EMG=Electromyography, SSEPs=Somatosensory Ewoked Potentials, TMS=Transcranial Magnetic Stimulation, MEPs=Motor Evoked Potentials, ES=Epidural Stimulation, TS=Transcutaneous Stimulation, BBS=Berg Balance Score, TUG=Timed Up and Go, 6MWT=6 Minute Walk Test, mFRT=Modified Functional Reach Test, ISNCSCI=International Standards of Neurological Classification of Spinal Cord Injury

^{2.} Further optimization may occur during training weeks 1-4.

Electrophysiology tests

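### Table 1 plans a baseline kinematic assessment in both arms, but Table 3, the collection schedule, has no pre-intervention mark for Kinematics

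*Combined protocol and SAP*

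**What the plan says.** Section 3.1, Table 1, shows the two halves of the sample. In both, the pre-intervention column lists "Clinical, Electrophysiology, Kinematic Assessments & Surveys". For the arm whose post-intervention column is legible, that column reads "End Assessments Clinical, Electrophysiology, Kinematic Assessments & Surveys".

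Section 3.2 declines to designate formal primary endpoints because this is a pilot, and then adds: "we do consider the biomechanical assessments and electrophysiology tests to be the primary sets of endpoints". Kinematics is one of the biomechanical assessments in section 6.6.1 and stands among the primary outcomes in Table 3.

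Section 6.6 gives Table 3 its authority: "The following outcome measures will be collected as scheduled in" that table. Its Kinematics row is marked at week 1, week 4 and the follow-up column (weeks 8 and 20). It is blank at Screening, Pre (baseline) and Post (week 5).

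Four other statements bear on whether a baseline exists:

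- Section 6.1: "When possible, eligible subjects will have their screening data used as baseline data collection".
- Section 6.6.1: "biomechanical assessment equipment may be used during select rehabilitation sessions in addition to the main assessment timepoints described in" Table 3.
- Table 3, footnote 2, attached to Kinematics: "Further optimization may occur during training weeks 1-4".
- Section 6.2: "Any visit to the laboratory when TS is enabled will be considered a training session". Section 6.4 has the same rule for ES. Both sections start training only once baseline tests are done.

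**The concern.** One table plans a kinematic recording before the intervention and the other does not schedule it. Staff working from the collection schedule would follow Table 3, and a recording missed before training cannot be made afterwards.

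Section 8.2 plans scatterplots of values before and after ES. It also plans models that relate baseline and first-month values to end-of-study values, partly to look for markers of response. Applied to kinematics, these need a value that is clearly pre-intervention. Section 8.2 lists baseline and the first month as separate things, so a week 1 recording is not obviously its baseline. With four subjects per arm, there is little room to lose a reference value.

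**Working it through.** The plan gives no figure to reproduce here. The check sets the two tables side by side and then asks whether other text closes the gap.

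**Step 1: read Table 3 by column.** The columns run Screening, Pre, Implant, weeks 1 to 4, Explant, Post (week 5), Follow-Up (weeks 8, 20). The alignment can be tested on Motor Training, which falls on weeks 1, 2, 3 and 4 as it should. Selected rows:

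| Row | Screening | Pre | Week 1 | Week 4 | Post (5) | Follow-Up (8, 20) |
|---|---|---|---|---|---|---|
| Kinematics | – | – | X | X | – | X |
| EMG | – | X | X | X | X | X |
| SSEPs | – | X | – | – | X | X |
| ISNCSCI | X | – | – | – | X | X |
| FRT/mFRT | – | – | X | X | – | X |

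EMG, the next row and also a biomechanical measure, has the Pre mark that Kinematics lacks.

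**Step 2: compare with Table 1.** Table 1 has one kinematic assessment before the intervention; Table 3 has none.

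**Step 3: look for text that supplies the value.**

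- Section 6.1 lets screening data stand in for baseline, but Table 3 gives Kinematics no Screening mark. The same section names biomechanical assessments as primary outcomes, which leans towards Table 1 without scheduling anything.
- The extra recordings allowed in section 6.6.1 take place in rehabilitation sessions, and footnote 2 concerns weeks 1 to 4. Neither is pre-intervention.
- Week 1 is a training week. No statement puts its testing ahead of the first session, and a test with stimulation on counts as a session.

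**Step 4: size.** Inputs: 8 subjects, 4 per arm (section 4); one baseline assessment each (Table 1). Planned baseline kinematic assessments without a Table 3 mark: 4 × 1 + 4 × 1 = 8.

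**Step 5: what week 1 could represent.** Assume 3 sessions a week for 4 weeks (3 × 4 = 12) and testing at any point in the marked week.

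- Sessions before the week 1 test: 0 to 3, so 0/12 = 0% to 3/12 = 25%. Only the zero case is a pre-training value.
- Sessions before the week 4 test: 9 to 12.
- Sessions spanned from week 1 to week 4: at least 9 − 3 = 6 (50%), at most 12 − 0 = 12 (100%).

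**Step 6: what is unaffected.** Retention windows from week 4 are 8 − 4 = 4 weeks and 20 − 4 = 16 weeks. The latter matches the 16-week post-stimulation objective in the Study Summary.

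**The case against.** The best defence is that Table 3 is deliberate. The Study Summary and section 2 ask about outcomes during four weeks of stimulated training, change over 12 sessions, and retention for 16 weeks afterwards. Marks at weeks 1, 4, 8 and 20 serve those aims, and none of them names a pre-intervention kinematic contrast. On this view Table 1 is only an overview with one loose word. Section 6.6.1 also words the kinematic recordings permissively, and section 3.2 stops short of designating endpoints. Much of this stands: the consequence is limited, and the error may lie in Table 1. It does not remove the conflict, because one table still has to change.

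A reader might go further than the documents allow in four ways:

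- That no pre-intervention kinematic data will exist. The week 1 test may precede the first session, or staff may follow Table 1. The documents leave this open.
- That the end assessment is missing too, which would raise the count above 8. Table 1 gives its end assessment no week, and Table 3 marks Kinematics in week 4, the last training week. Week 4 could be that assessment, so this is an ambiguity.
- That FRT/mFRT is contradicted in the same way. It has the same marks, and section 6.6.1 records the mFRT by motion capture, but Table 1 does not name it.
- That section 8.2 promises a kinematic change-from-baseline analysis. It never names kinematics; its worked example is SSEPs, which have a Pre mark.

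**Conclusion.** Tables 1 and 3 contradict each other on baseline kinematics, and no other text settles the matter. Followed as written, Table 3 leaves up to 8 planned baseline assessments, one per subject, unscheduled within what section 3.2 considers a primary set of endpoints. Any analysis of kinematics under section 8.2 that needs a before value would have no clear one. The effect is confined to contrasts with the pre-intervention state.

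The count assumes 8 subjects as planned, with no replacements. It is an upper limit because some week 1 tests might precede the first session. The session ranges rest on the assumption that testing can fall anywhere in the marked week; they show how loosely week 1 is defined and do not establish an error. Table 1 is partly garbled in the available text, but its baseline entries are readable for both arms. This should be corrected before subjects reach baseline testing.

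**What to change.** Add a Pre mark for Kinematics in Table 3, at the visit where EMG is already recorded. State whether week 1 testing precedes the first stimulation session. Say whether week 4 or Post (week 5) is the end kinematic assessment of Table 1, and add a Post mark if it is Post.

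If weeks 1 and 4 are the intended schedule, correct Table 1 instead and name week 1, before the first session, as the kinematic reference for section 8.2. Under that choice the ES reference would follow lead implantation, since Implant comes before week 1 in Table 3; the TS arm has no such step. The protocol should acknowledge this.

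A Pre mark for FRT/mFRT is an optional parallel change.

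The cost is one or two marks, one or two sentences and a slightly longer Pre session, within the roughly one-week window that section 6.6 allows for each time point.
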